#### **3.3.3 Secondary Objectives**

##### **3.3.3.1 Key Secondary Objectives**

When and what type of health care services do participants in this study access, how frequently and is there a difference and between the two groups.

[figure not shown]

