#### **3.5.5 Secondary Outcome Measures**

For the secondary endpoints, we will analyze the frequency and type of health care patients accessed outside of their current standard of care during the 12-week study period. This will be compared to our controls and will include emergency room, family physician visits, hospital admissions and telehealth that are related to post traumatic headache symptoms.

Another end point we are interested in exploring is whether patients that are provided targeted headache education along with tertiary care has an increased frequency of social interactions in comparison to patients receiving the current standard of care. We are very interested in the hours that each patient devotes to their previous work or hobbies and we will be comparing this once again to patients in the clinic who are receiving the standard of care. This outcome will be measured using the PART-0 tool which asks questions about the type and frequency of social engagements that patients may encounter each week along with the hours that patients devote to returning back to work, school or homemaking.

Lastly, we are interested in whether or not education and reassurance alter a patient's perceived quality of life after a mild-traumatic brain injury. This will be analyzed by using the QOLIBRI (Quality of Life after Brain Injury). Using this scale we hope to capture whether or not patients believe they play an active role in their health and whether or not they feel empowered to alter their health status. It will hopefully also allow us to capture what

barriers there are to a patient's recovery in regard to what negative feelings and limits they perceive; preventing them from making a meaningful recovery.

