### **3.7 Methods: Data collection, management and analysis**

#### **3.7.1 Data Collection**

For all visits each patient will fill out a questionnaire (See Appendices for full surveys) using RedCap. If a patient is unable to enter the data using email directly, one of our research assistants will enter the data into the RedCap system via telephone interview. For the follow up survey if there is no response, we will attempt to contact the patient by phone three times. In regard to those patients seen in follow up in the clinic, we will ensure that they finish their follow up questionnaires after being seen by a healthcare professional to avoid unblinding. Patients' receiving the standard of care will be asked the same questions at week 0 and 12 with the same surveys as the education intervention arm of the study. A secure password protected master linking log will be able to house the patient name with study identification number.

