#### *Access to Medical Services*

Tracking patient's utilization of health care services during the time of the study is an important outcome that this study hopes to measure. The aim is to see if education can ultimately reduce unnecessary access to medical care. As stated previously we hope to accomplish this by providing information to patients on red flags and when to seek medical advice. Patients will be asked to recall the number of times they have sought out medical attention since they were last seen in the subspecialty clinic. This includes walk-in clinics, hospitals, their family MD, telehealth and ER visits. Future goals after this study has been completed would be to use the ICES database to quantify the utilization of health care services in this subset patient population.

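### Health-care use, the key secondary outcome, is defined over the 12-week study period, but patients recall contacts only since their last clinic visit

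*Protocol*

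**What the plan says.** Section 3.3.3.1 has one key secondary objective: "When and what type of health care services do participants in this study access, how frequently", and whether the arms differ. Section 3.5.5 sets the outcome window: "we will analyze the frequency and type of health care patients accessed outside of their current standard of care during the 12-week study period". The paragraph on Access to Medical Services in section 3.7.4 opens with the same window, "utilization of health care services during the time of the study", and then gives the collection rule: patients are asked to "recall the number of times they have sought out medical attention since they were last seen in the subspecialty clinic".

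Other sections bear on how that rule would work:

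- Section 3.5.2.1 allows for patients coming back to the clinic during the study. Section 3.7.1 has patients seen in clinic follow-up complete the follow-up questionnaire after they have been seen.
- Section 3.7.1 begins "For all visits each patient will fill out a questionnaire", but then says that standard-care patients "will be asked the same questions at week 0 and 12 with the same surveys" as the education arm. Section 3.5.2.2 also puts the control surveys at weeks 0 and 12.
- Access to Medical Services leaves the administrative database to work after this study, so patient recall is the only stated source.

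The two descriptions also differ in what they count. Section 3.5.5 covers emergency room and family physician visits, "hospital admissions and telehealth that are related to post traumatic headache symptoms", and does not name walk-in clinics. Access to Medical Services states: "This includes walk-in clinics, hospitals, their family MD, telehealth and ER visits", with no limit to headache. Section 3.1 names walk-in clinics among the visits the trial hopes to reduce.

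**The concern.** The outcome has a fixed window, the same for everyone. The recall rule has a start date that moves with each patient's clinic attendance. A patient who returns to the clinic during follow-up is, as the rule is worded, asked only about the time after that return, and any contact between enrolment and the return goes uncounted.

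This cannot be repaired in the analysis. A contact that was never asked about is not in the data. The rule as described collects a number of contacts and no dates, although the objective also asks when services were used, so counts over unequal periods could not be realigned to 12 weeks afterwards. For that reason the point belongs in the protocol and on the survey form, and cannot be left to the statistical analysis plan.

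**Working it through.** The plan states no figure to reproduce. The check compares the two windows and then works out what the difference would cost.

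**Step 1: the two windows.**

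| | Start | End | Length |
|---|---|---|---|
| Outcome (section 3.5.5) | week 0 | week 12 | 12 weeks |
| Recall (Access to Medical Services), asked once at week 12 | last clinic visit, week *w* | week 12 | 12 − *w* weeks |

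They are equal only when *w* = 0.

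**Step 2: coverage for one patient**, (12 − *w*)/12:

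- *w* = 0: 12/12 = 100%
- *w* = 3: 9/12 = 75%
- *w* = 6: 6/12 = 50%
- *w* = 9: 3/12 = 25%
- Clinic visit on the day of the week-12 survey: about 0%, if the rule is read literally, because section 3.7.1 puts the questionnaire after the visit.

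**Step 3: coverage across patients.** Let *p* be the share of patients with a return visit, with the last one at week *w*. Assume a constant contact rate that does not depend on returning. Then

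captured share = (1 − *p*) × 1 + *p* × (12 − *w*)/12 = 1 − *p* × *w*/12.

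The protocol gives neither *p* nor *w*, so both are assumed:

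| Last visit | *p* = 20% | *p* = 50% | *p* = 80% |
|---|---|---|---|
| week 3 | 95% | 87.5% | 80% |
| week 6 | 90% | 75% | 60% |
| week 9 | 85% | 62.5% | 40% |

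For example, at week 6 with *p* = 50%: 1 − 0.5 × 6/12 = 0.75.

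**Step 4: the reading with no loss.** If the question were asked at every clinic visit and again at week 12, and the periods were added, coverage would be *w* + (12 − *w*) = 12 weeks, or 100%. The same holds for *p* = 0. The loss therefore lies between 0 and *p* × *w*/12, depending on a reading that the protocol does not settle.

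**Step 5: the comparison between arms.** If the same share returns in both arms, capture is the same in both. With 50% returning at week 6 it is 0.75 in each, and the apparent rate ratio under equal true rates is 0.75/0.75 = 1.00. The ratio is distorted only if returns differ by arm.

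**The case against.** The strongest reply is that the recall sentence is loose shorthand. The only fixed in-person contact is the week 0 session, return visits are conditional, and the paragraph opens with the study period. The last clinic visit could therefore simply mean enrolment, which gives exactly 12 weeks. The most literal reading leaves a patient surveyed just after a visit with almost nothing to recall, which suggests that it was not intended. The opening of section 3.7.1 could also support rolling recall at every visit. The forms listed in section 3.9 are not shown, and the actual survey item may carry a correct time anchor.

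These readings are possible, but none is stated. The sentence does not mention enrolment. Rolling recall fits poorly with control surveys at weeks 0 and 12 only, and no section says that periods are summed or on which form and when the question is asked. What stands is that the loss may be zero and that the finding concerns the written rule, not the unseen form.

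Two further objections also stand in part. The percentages rest on assumed return shares and timings, so they show a range and do not estimate the loss. No bias between arms is shown: section 3.5.2.5 (clinicians blinded, the same standard care) gives some reason to expect similar returns. On the service lists, neither claims to be complete, so that mismatch is minor.

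**Conclusion.** The concern holds. The protocol defines its key secondary outcome over 12 weeks and gives a recall rule that can cover less, over periods that differ between patients. Under a single week-12 question, a patient last seen at week 3, 6 or 9 has 75%, 50% or 25% of the window covered. Across patients the captured share runs from 95% (20% returning, week 3) down to 40% (80% returning, week 9), and it is 100% if nobody returns or if rolling periods are summed.

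These figures assume a constant contact rate and return patterns that the protocol does not give. The conclusion is that the outcome is not measured as defined. It does not extend to a biased comparison between arms, and it does not touch the primary Rivermead comparison. Confidence is moderate, because the survey form could settle the matter either way.

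**What to change.** In Access to Medical Services (section 3.7.4), anchor recall at enrolment: at the week-12 survey, ask both arms about contacts from week 0 to week 12, and state that clinic visits in between do not reset the period. Alternatively, ask at every contact on the same schedule in both arms, and state that the non-overlapping periods are summed.

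In either case, say which form carries the question and check that the follow-up survey item matches. Use one service list, including walk-in clinics, and one rule on relatedness to headache in sections 3.5.5 and 3.7.4.

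The cost is about one sentence, one aligned list and a check of one survey item. The first option gives everyone a 12-week recall period, a small drawback. The second shortens recall but needs extra questions, asked on the same schedule in both arms.

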#### **3.7.5 Retention**

All subjects will be offered compensation in the form of a Tim Horton's gift card.

#### **3.7.6 Data Management**

All research data will be entered into a de-identified database and kept on a secure server at St. Michael's hospital.

#### **3.7.7 Statistics**

The IBM SPSS statistical software will be used for the data analysis. Data will be entered on demographic factors (sex, age, ethnicity, years of education), frequency and type of health care accessed will be analyzed as well. Scores on the Rivermead, PART-O and QUOLIBRI will be analyzed and comparisons will be made between the educational arm and the current standard of care group. We will be using univariate Chi-square analysis for categorical variables and 1 way analysis for continuous variables to assess for significant difference. P-value of <0.05 will be considered as statistically significant.

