By the end of the study, the educational intervention group will be more satisfied in various aspects of their life as measured by the QOLIBRI compared to their week 0 scores.

*Endpoints of the study:* Significance will be observed if patients reported symptoms decrease by 3 points on the RPQ-3 and 10 on the RPQ-13.

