##### **3.3.3.2 Other Secondary Objectives**

- Does education through reinforcement of appropriate lifestyle and treatment strategies translate to similar pre-injury scores on the PART-0 tool at the 12-week time point.
- By the end of the study, the educational intervention group will be more satisfied in various aspects of their life as measured by the QUOLIBRI compared to their week 0 scores.

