### **3.5.6 Sample Size**

Sample size is based on alpha (2-sided significant level) of 0.05 and power of 80%. Given that the largest review study (Theeler, 2013) showed a headache prevalence of 21-100% (0.21 – 1.00) in their TBI group and 26% (0.26) in the control group with a ratio of control/cases= 1:1, sample size was computed at 28 (Educational group) and 28 (standard of care group) with total sample size of 56. We have anticipated 20% attrition and therefore we will aim to enroll 35 patients per study arm in order to maintain statistical significance. This rate is based on prior studies using the RPQ and a recent study conducted at St. Michael's by Hu et al. looking at age and association with mild-traumatic brain injury symptoms.

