### ***3.7.3 Primary Outcomes.***

Data will be collected using the Rivermead Post Concussion Symptoms Questionnaire (RPQ): The symptoms listed on the RPQ are those most commonly reported in the published literature as post concussion syndrome (PCS). The RPCSQ is a 16-question instrument that examines post-concussion symptoms rated by the patient according to the increase in their frequency compared with premorbid levels. The total score is calculated based on 2 domains (cognitive and emotional-somatic) and ranges from 0 to 72. The RPQ has been shown to measure severity of postconcussion symptoms reliably with good test-retest and inter-rater reliability for individual symptom scores. Based on previous studies, splitting the RPQ into two subscale scores: RPQ-3 uses the sum of scores from three items

(headaches, dizziness and nausea) and RPQ-13 uses the sum of scores of the other 13 items. Higher scores especially for the RPQ-13 subscale are associated with greater impact on lifestyle. For our study significance will be observed if patients reported symptoms decreased by 3 on the RPQ-3 and 10 on the RPQ-13.

We will be comparing headache symptom reporting between the two groups assigning significance if patients in the education arm have a decrease in symptom reporting on the RPQ-3 by 3 and 10 on the RPQ-13.

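### Section 3.7.7 compares RPQ, PART-O and QOLIBRI between arms by a one-way analysis that leaves out the week-0 scores and does not say whether week-12 or change scores are tested

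*Protocol*

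**What the plan says.** Section 3.7.7 gives the whole analysis of the questionnaire scores. It says that "comparisons will be made between the educational arm and the current standard of care group", and then names the methods: "We will be using univariate Chi-square analysis for categorical variables and 1 way analysis for continuous variables to assess for significant difference". The one-way method is presumably one-way ANOVA. No covariate, time point or change score is mentioned.

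Week-0 scores will exist for both arms. Section 3.5.2.2 has RPQ, PART-O and QOLIBRI completed before the first session, and section 3.7.1 says that standard-of-care patients "will be asked the same questions at week 0 and 12 with the same surveys as the education intervention arm".

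Other sections point to different contrasts:

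- **RPQ.** Section 3.7.3 assigns significance if education-arm patients "have a decrease in symptom reporting on the RPQ-3 by 3 and 10 on the RPQ-13". This leans towards change from week 0. Section 3.3.2 sets the same decrease against patients who do not receive the education.
- **QOLIBRI.** Section 3.3.3.2 and the Protocol Summary state that "the educational intervention group will be more satisfied in various aspects of their life as measured by the QUOLIBRI compared to their week 0 scores". That is a within-arm contrast, whereas section 3.7.7 plans a between-arm one.

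**The concern.** A one-way comparison has no place for the baseline score. In a small trial with a patient-reported scale measured at both ends, this costs precision for no saving, because the baseline is collected anyway.

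The arms will also differ at week 0 by chance. A week-12-only test carries part of that difference into the treatment estimate in one direction. A change-score test carries part of it in the other direction. Adjustment for the week-0 score removes the shift under either reading.

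Because the tested score is not named, either version could be chosen once results are visible, and the two can differ materially in power.

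**Working it through.** **Inputs from the protocol.** Section 3.5.6: "sample size was computed at 28 (Educational group) and 28 (standard of care group) with total sample size of 56", two-sided alpha 0.05, power 80%, 20% attrition. The attrition step reproduces: 28 / (1 − 0.20) = 35 per arm, 70 in total. The 28 itself does not follow from either end of the stated prevalence range: 0.21 against 0.26 needs 1128 per arm, and 1.00 against 0.26 needs 6 (two-sided, no continuity correction). That is a separate matter, and 28 is used here only as the planned number of evaluable patients per arm. Since it was derived from headache prevalence, it supplies no SD and no correlation for the questionnaire scores.

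**Assumptions.** Correlation r between the week-0 and week-12 scores of 0.4, 0.5, 0.6 or 0.7, with 0.3 added as a low case; equal SDs at both times. Results are in units of that SD.

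**Variance of the arm difference, relative to a week-12-only test (= 1).**

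- Change score: 2(1 − r)
- Baseline-adjusted (ANCOVA): 1 − r²
- Cut from adjustment against week-12 only: r²
- Cut from adjustment against change: 1 − (1 − r²) / [2(1 − r)] = 1 − (1 + r)/2

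The equivalent gain in patients is 1/(1 − r²) against week-12 only and 2/(1 + r) against change.

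**Chance imbalance.** The SD of the week-0 mean difference is √(2/28) = 0.267 SD. An imbalance of that size shifts the week-12 difference by r × 0.267 and the change-score difference by (1 − r) × 0.267 in the opposite direction.

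**Detectable difference.** Noncentral t, two-sided 5%, 80% power, 28 per arm; 54 degrees of freedom, or 53 for ANCOVA with its variance multiplied by 1 + 1/(2 × 28 − 4) = 1.019 for estimating the covariate.

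| r | 0.3 | 0.4 | 0.5 | 0.6 | 0.7 |
|---|---|---|---|---|---|
| Variance, change score | 1.40 | 1.20 | 1.00 | 0.80 | 0.60 |
| Variance, ANCOVA | 0.91 | 0.84 | 0.75 | 0.64 | 0.51 |
| Cut against week-12 only | 9% | 16% | 25% | 36% | 49% |
| Cut against change | 35% | 30% | 25% | 20% | 15% |
| Patients, against week-12 only | ×1.10 | ×1.19 | ×1.33 | ×1.56 | ×1.96 |
| Patients, against change | ×1.54 | ×1.43 | ×1.33 | ×1.25 | ×1.18 |
| Detectable, week-12 only (SD) | 0.76 | 0.76 | 0.76 | 0.76 | 0.76 |
| Detectable, change (SD) | 0.90 | 0.84 | 0.76 | 0.68 | 0.59 |
| Detectable, ANCOVA (SD) | 0.73 | 0.71 | 0.67 | 0.62 | 0.55 |
| Shift, week-12 only (SD) | 0.08 | 0.11 | 0.13 | 0.16 | 0.19 |
| Shift, change, opposite sign (SD) | 0.19 | 0.16 | 0.13 | 0.11 | 0.08 |

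With the 1.019 factor, the variance cuts for r = 0.4 to 0.7 become 14, 24, 35 and 48% against week-12 only, and 29, 24, 18 and 13% against change. ANCOVA remains the most precise of the three at every r shown.

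**Power for a fixed effect.** By the normal approximation, a week-12-only test at 28 per arm has 80% power for 0.749 SD. For that effect the change score has 66% power at r = 0.3, 80% at r = 0.5 and 95% at r = 0.7. ANCOVA has 84%, 90% and 98%. The choice left open is therefore consequential.

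**The case against.** **This is SAP detail.** An SAP may exist, and silence on the tested score alone could be left to it. That much stands. But section 3.7.7 is not silent on method: it names a one-way analysis, and that is a choice which can be judged. It is fair to add that the word univariate in that sentence attaches most directly to the chi-square test, so the point rests on the one-way wording.

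**Change from week 0 is the natural reading for RPQ.** This is reasonable, and the week-12-only rows would then drop out for that scale. The gain over change remains: 30 to 15% of the variance for r = 0.4 to 0.7.

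**The decrease could be a per-patient threshold.** The outcome would then be categorical, chi-square would apply, and the figures above would not. The wording allows this reading, but section 3.7.7 speaks of comparing scores, and section 3.3.2 frames the decrease as a comparison between groups.

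**The size rests on an assumed r.** It does, and r may differ across the scales. At r = 0.3 the gain over a week-12-only test is small (0.73 against 0.76 SD), although against change it is then at its largest.

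**Analysts are to work without the allocation.** Section 3.6.2 plans this. It lessens the risk of a choice made after the data are seen but does not remove it.

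**Timing.** Section 3.5.2.2 can be read as placing the education arm's final questionnaires one week after the week-12 session. This does not affect the use of the week-0 score.

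**Conclusion.** The concern holds and should be acted on. The planned one-way test is valid under 1:1 randomisation. What it gives up is precision and protection against chance imbalance at 28 evaluable patients per arm, where a typical week-0 difference is 0.27 SD. For assumed correlations of 0.4 to 0.7 and equal SDs, adjustment is worth 1.19 to 1.96 times the patients against a week-12-only test and 1.43 to 1.18 times against a change-score test. The direction does not depend on which score was intended; the size does depend on a correlation that the protocol does not give. The mismatch between the QOLIBRI objective and section 3.7.7 is a secondary wording point.

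**What to change.** In section 3.7.7, replace the one-way analysis for these scales with: *The week-12 RPQ-3, RPQ-13, PART-O and QOLIBRI scores will each be analysed with a linear model on arm and the same scale's week-0 score; the adjusted between-arm difference will be reported with its 95% CI.*

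With the week-0 score in the model, the arm difference is identical whether the outcome is the week-12 score or the change. One sentence therefore settles which score is tested, and the estimate can be read against the 3- and 10-point figures as a between-group difference.

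Reword the QOLIBRI objective in section 3.3.3.2 and the Protocol Summary as the between-arm comparison that section 3.7.7 already plans.

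Two matters stay open and need their own resolution: the PART-O objective about pre-injury scores, and the use of point decreases alongside p < 0.05 as the mark of significance.

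The cost is the wording of one section and one secondary objective, with no new data, visits or software.

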### **3.8 Ethics and dissemination**

#### **3.8.1 Ethics**

If the patient is interested in this study, they will receive the consent form explaining the purpose, procedure and requirements of the project from trained research assistants who will be available to answer questions regarding the project. Informed consent will be obtained from patients who will meet the eligibility criteria and agree to participate.

If the participant cannot sign and date the consent form properly they will be asked to provide consent with an "X", their initials or by signing with their alternate hand. If the participant is completely unable to provide written consent they will be asked for verbal consent and research staff obtaining consent will document the discussion on the consent form. Initial information will be extracted from the medical record including age, medical history, imaging results, Glasgow coma scale and neurological examination. Patients who agreed to participate will be asked to complete a demographic questionnaire, the Rivermead Post Concussion Symptom Questionnaire, the QUOLIBRI and the PART-O in person for the first session and then either again in person or by telephone interview.

Participant involved in the educational arm of the study must have email and easy access to a computer. When they are randomized they will be asked for their email address.

Participants will be given their study ID number when they consent. They will be asked to use this number as their ID on the survey. Follow up at 7 weeks will occur with the education arm 1 week after they have been emailed the power point material.

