#### 3.4.1 Post Traumatic Headache Education Study Flow Diagram

**3.4.1.1 *Figure 1: Flow diagram of patient enrollment, allocation and follow up.***

## **3.5 Methods: Participants, Measures and Outcomes**

### **3.5.1 Eligibility Criteria**

#### **3.5.1.1 *Inclusion Criteria***

Inclusion criteria will be individuals between the age of 18- 65 years of age with a chronic mTBI based on CDC criteria. They must have the ability to give consent, speak English with awareness that they will need to be contacted at various time points, and must have access to email. We will include patients that score 3 or more on the RPQ either in the ER or during their initial assessment. They must be medically stable.

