### **3.5.2 Interventions**

#### **3.5.2.1 *Educational Intervention***

Participants in the education arm of the study will be provided with three PowerPoint presentations. Material for these slides has been adapted from material developed by the Ontario Neurotrauma Foundation. Topics to be addressed will surround post-traumatic headache and will include information regarding common symptoms, timeline for improvement, red- flags and when to seek medical attention. The first session is conducted in-person to provide participants with an outline of the study and to discuss the first PowerPoint session. For the remainder of the sessions, the PowerPoint slides will be emailed with follow up telephone or in person discussions with patients to ensure that they received the material, understood it and could open it. At the 12-week time point (post study enrollment) we will also ensure that patients have filled out the survey's via REDCap and perform an Exit interview. If patients return to the clinic for subsequent follow up visits, we will attempt to provide the session at the follow up visit that closely relates to the time point stated above.

For those patients not allotted to the education arm, at the end of the study they will be offered the educational material should they wish to review it.

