**3.5.2.2 Summary of education by session: PowerPoint slides will be split into three distinct sections.**

*Initial session: (0 weeks): (In person)* We will outline the study. Approximately 30 minutes in duration.

[figure not shown]
- Review inclusion/exclusion criteria
- Explain study goals
- Obtain written/verbal informed consent
- We will cover topics such as defining the basic anatomy and the consequences of head trauma. We will include common symptoms along with when to seek medical guidance, medications to avoid and helpful lifestyle and treatment tips. Patients will be provided with links to approved websites.
- Prior to this session
  - Complete demographic information, medical history, trauma history and participant contact information (email or phone) will be gathered. If patients are identified in the ER, this information will be provided by the Triage nurse and forwarded to the research assistant who will be responsible for follow-up and providing the study materials.
  - Rivermead Post-Concussive Questionnaire (RPCSQ), PART-O and QOLIBRI (Yellow form: See Appendix) will be completed.
- *Second Session (6 weeks): (via email)*. Explain importance of keeping brain active; define the assessment of brain activity. 10-20 minutes to review the PowerPoint. Follow up will be done 1 week later either in person, email or via telephone to ensure patients are able to open the PowerPoint and have reviewed the literature. There will be no education or discussion about current treatment regimen or symptoms. Should a patient have questions regarding their current treatment plan or symptoms, our volunteers will put patients in contact with the Head Injury Nurse. All calls will be made during clinic hours in order to help facilitate communication with the clinic.

*Third Session (12 weeks)- (In person or sent via email)* We will explain importance of stress, sleep, and exercise on brain function, define the influence of lifestyle on recovery.

Approximate duration is 10-20 minutes. 1 week later follow up via telephone or email will occur by the methods listed above to ensure that the patient was able to open the PowerPoint. At this time we will:

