- Re-verify inclusion criteria to be done by Research Assistant. There will be no education or discussion about current treatment regimen or symptoms. Should a patient have questions regarding their current treatment plan or symptoms all calls will be made when the Head Injury Nurse is available to connect with patients directly.

- Rivermead Post-Concussive Questionnaire (RPCSQ), PART-O and QUOLIBRI will be completed via telephone or email and entered via REDCap into our database. Survey data will be uploaded by student or research assistant that is unaware of the patient's randomization.
- The patients who did not participate in the education seminar will fill out surveys at week 0 and 12.

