## **3.6 Methods: Assignment of Intervention**

### **3.6.1 Allocation**

Participants will be randomly assigned to either control or interventional group with a 1:1 allocation as per a computer-generated randomization schedule using permuted blocks of random sizes. The block sizes will not be disclosed, to ensure concealment. The research assistant will not be allowed to touch the randomizing envelopes until each patient is about to be randomized.

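### Section 3.8.1 requires easy computer access of the education arm only, so as written the condition can be applied only after allocation and in one arm

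*Protocol*

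**What the plan says.** Protocol 3.5.1.1 (Inclusion Criteria) applies to everyone and says that patients "must have access to email". It does not mention a computer.

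Protocol 3.8.1 (Ethics) adds a requirement for one arm: "Participant involved in the educational arm of the study must have email and easy access to a computer". The next sentence reads "When they are randomized they will be asked for their email address".

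Other sections bear on when and how this matters:

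- 3.5.2.2, on what is collected before the initial session: "participant contact information (email or phone) will be gathered".
- 3.5.2.1, on sessions after the first: "the PowerPoint slides will be emailed with follow up telephone or in person discussions with patients".
- 3.7.1, on outcome data: "If a patient is unable to enter the data using email directly, one of our research assistants will enter the data", by telephone interview.
- 3.6.1, on allocation: patients are "randomly assigned to either control or interventional group with a 1:1 allocation".
- 3.5.2.2, third session: "Re-verify inclusion criteria to be done by Research Assistant". No consequence of failing is given.

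**The concern.** A condition that decides who may take part should be the same for both arms and settled before allocation. Here the computer condition is attached to membership of the education arm, which exists only once a patient has been randomised. Two patients alike in every respect, both with email and neither with easy use of a computer, would be treated differently. The one allocated to education fails a stated requirement, and the one allocated to standard care never meets it.

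What is at stake depends on something the protocol leaves open. If the requirement were enforced by withdrawing or replacing patients, the education arm would be selected after randomisation and the control arm would not. Computer access could plausibly go with work and schooling, and PART-O counts hours given to both. If the requirement were not enforced, some education patients would be unable to open the emailed slides, and the contrast between the arms would be weakened.

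**Working it through.** The protocol gives no figure on this point, so the main check is a comparison of the text.

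**Requirement by arm**

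| Requirement | Education arm | Standard-care arm |
|---|---|---|
| Email access | Yes (3.5.1.1; repeated in 3.8.1) | Yes (3.5.1.1) |
| Easy computer access | Yes (3.8.1) | Not stated anywhere |

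Only computer access differs between the arms.

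**Timing.** No section describes a check of computer access before the envelope is opened. The contact details gathered beforehand under 3.5.2.2 may be an email address or a telephone number, so even the common email criterion need not have been documented by then.

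**Need for a computer.** Session 1 is in person. Session 2 is described as sent by email. Session 3 is in person or by email. Section 3.5.2.1 also allows a session to be given at a clinic follow-up visit. Outcome data can be taken by telephone. A patient without a computer can therefore supply outcomes in either arm and may miss only part of the education.

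**Illustration of size (assumed inputs, not protocol figures)**

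Protocol inputs (3.5.6): 28 per arm, 20% attrition, two-sided alpha 0.05, 80% power. The enrolment figure reproduces: 28 / (1 − 0.20) = 35 per arm.

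The protocol sizes the trial on proportions. To have a scale for continuous scores, the standardised difference detectable with 28 per arm (normal approximation) is (1.960 + 0.842) × √(2/28) = 0.75 SD.

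Let f be the assumed share of the education arm without easy computer access, and m the assumed outcome gap, in SD, between those patients and the rest of the arm.

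*If they are removed:*

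- Shift in the between-arm difference = f × m.
- Education patients remaining after attrition = 35 × (1 − f) × 0.80, against 28 controls. Power is evaluated at 0.75 SD.

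| f | Left of 35 | After 20% attrition | Power | Shift, m = 0.5 | Shift, m = 1.0 |
|---|---|---|---|---|---|
| 0% | 35 | 28 | 80% | 0 | 0 |
| 5% | 33.25 | 26.6 | 79% | 0.025 SD | 0.05 SD |
| 10% | 31.5 | 25.2 | 78% | 0.05 SD | 0.10 SD |
| 20% | 28 | 22.4 | 75% | 0.10 SD | 0.20 SD |

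The shift favours education only if those removed would have done worse. If they would have done better, it goes the other way.

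*If they are kept and, at the extreme, gain nothing:*

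- Observed effect = (1 − f) × true effect.
- For a true effect of 0.75 SD: 0.95 × 0.75 = 0.71 SD, 0.90 × 0.75 = 0.675 SD, 0.80 × 0.75 = 0.60 SD for f of 5%, 10% and 20%.
- The real dilution should be smaller, since session 1 is given face to face.

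**The case against.** The strongest reply is that the harm is not in the document. No section says that a patient without a computer is withdrawn, replaced or left out of the analysis. A reader might infer from the word must in 3.8.1 that the protocol runs a screening step after randomisation. The text does not support that, and the rule on who is analysed may stand in an analysis plan that is not at hand. This part of the reply stands: one-sided selection is a risk that the wording leaves open, and it is not a stated procedure.

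A reader might also take the re-check of inclusion criteria around week 12 as the mechanism for exclusion. It is not, because it refers to the inclusion criteria and those do not list a computer.

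Nor is asking for the email address at randomisation an arm-specific condition. Email is already required of everyone, and the sentence reads most naturally as collecting a delivery address for the slides.

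It can further be said that candidates are told the project's requirements at consent, so the computer requirement may be raised with all of them beforehand. The consent pages are not in the copy reviewed, so this can be neither confirmed nor ruled out. The in-person and telephone routes also reduce the dependence on a computer.

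What remains after all this is the mismatch itself. One arm carries a requirement that the eligibility list does not contain, with no stated time of checking and no stated consequence.

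**Conclusion.** The point holds as an inconsistency between 3.5.1.1 and 3.8.1 that should be corrected. Computer access is demanded of one arm only, so as written it can be applied only after allocation. The outcome for a patient who lacks it is unspecified: removal would give selection in one arm, and retention would give non-adherence that dilutes the effect.

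The size is unknown and probably small, since every patient has email. The illustrative shifts of 0.025 to 0.20 SD rest wholly on assumed shares of 5% to 20%, assumed gaps of 0.5 to 1.0 SD, and complete removal of the patients concerned. None of these comes from the protocol. They show that the effect would be modest beside 0.75 SD, and they do not estimate an actual bias. It would be wrong to conclude that the trial is biased in favour of education.

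**What to change.** 1. In 3.5.1.1, make email and easy computer access a criterion for every patient.
2. Confirm and record it before the randomisation envelope is opened. Bring the contact-details line in 3.5.2.2 into agreement, so that an email address is on file for everyone by then.
3. Delete the arm-specific sentence in 3.8.1.
4. State that every randomised patient stays in the analysis in the arm allocated, including any education patient who later cannot open the material. If the analysis plan already says this, a cross-reference is enough.

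The cost is small: a few edited sentences and one extra item on the screening form. A few patients without a computer would be screened out before randomisation, and the trial population would be slightly narrower.
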